3.2.2.2 Alternate baseline

Due to the severity of disease in hospitals and the pandemic conditions some participants may not have a baseline recorded prior to their first dose. In the event there is no measurement at all prior to dosing for the key parameters then a measurement up to 2 hours postdose (this time frame may change based on PK/PD data) may be included as baseline for that participant. This baseline will be referred to as the ‘alternate baseline’ and will be used in sensitivity analyses.

3.3 Protocol deviations

Important protocol deviations are deviations from the protocol which potentially could have a meaningful impact on study conduct or on the primary efficacy (effectiveness) or safety for an individual participant. The criteria for identifying important protocol deviations may be defined within the appropriate protocol-specific document. Important protocol deviations will be reviewed as part of the ongoing data cleaning process and data evaluation documented in a protocol deviation log. All important deviations will be identified and documented prior to final database lock to confirm exclusion from analysis sets.

Note: whilst protocol deviations maybe listed for Interim1 it is unlikely sufficient determination on the effect of the deviations will have been reviewed and hence no one will be excluded from the PPS (section 3.5.6) for Interim1.

3.4 Treatment assignment and treatment groups

Participants will be randomized onto one of the two treatment arms (Arm A: Zilucoplan®+SOC, Arm B: SOC only) in a 2:1 ratio. The 2:1 randomisation will be carried out using REDCap (electronic IWRS system) by centre. No other stratification factors are planned.

3.5 Analysis sets

All safety analyses will be carried out on the Safety Set. All efficacy analyses will be carried out on the Full Analysis Set. They may be repeated on the Randomised and Per Protocol Set if these are generated. PK analyses will be carried out on the Pharmacokinetic Analysis Set.

It is expected that participants will receive treatment as randomized. However, if it is determined that participants received treatment other than what they were randomized to, then all analysis sets participants will be allocated to the actual treatment they received (SS-as treated, FAS – as treated, RS – as treated, PPS, PKS – as treated).

It is always appropriate to assess safety and PK based on actual treatment received. Since this is a PoC study, it is appropriate that treatment assignment for the FAS will be also be actual treatment received.

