	
Time since randomization until first use of high-flow oxygen devices or non-invasive mechanical ventilation or invasive mechanical ventilation or ECMO in non-ventilated participants (i.e. excluding participants who are ventilated within 24h prior to or after randomization) during 28-day assessment period
	
Use Vital Parameter CRF,

	
Time since randomization to progression to ARDS
	
Randomisation date
 
Date of ARDS diagnosis

	
Duration of ICU stay in participants that enrolled in trial that were on invasive or non-invasive mechanical ventilation or high-flow oxygen devices within 24h prior to or after randomization during 28-day assessment period
 
Duration of ICU stay in participants that enrolled in trial that were on invasive or non-invasive mechanical ventilation for less than 24h prior to or after randomization during 28-day assessment period
	
Use DATES and Vital Signs dataset

Secondary Objective	Endpoint	Measurement

3) To study if treatment with Zilucoplan® affects all-cause mortality rate at day 28 and at 12-22 weeks post-randomisation
	
All-cause mortality rate at 28 days post randomisation (all treated participants)
 
All-cause mortality rate at 28 days post randomisation (excluding participants that required invasive mechanical ventilation or ECMO, non-invasive mechanical ventilation or high-flow oxygen devices within 24 hours prior to or after randomisation)
 
All-cause mortality rate at 28 days post randomisation (excluding participants that required invasive mechanical ventilation or ECMO within 24 hours prior to or after randomisation)
 
All-cause mortality rate at 28 days post randomisation (excluding participants that required invasive mechanical ventilation or ECMO, non-invasive mechanical ventilation or high-flow oxygen devices within 24 hours prior to or after randomisation)
 
All-cause mortality rate at 28 days post randomisation (only including participants that required invasive mechanical ventilation or ECMO within 24 hours prior to or after randomisation)
 
All-cause mortality at follow up 12-22 weeks post-randomisation for all treated participants
	
6-point ordinal scores, DATES and VITAL SIGNS datasets

Secondary Objective	Endpoint	Measurement

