Data listings containing documented and calculated data (eg, change from Baseline) may be generated if it supports the interpretation of any analysis. Unless otherwise stated, listings will be sorted by treatment arm, participant number within arm, parameter (if applicable), nominal day and relative day respective to first dose and relative day with respect to last dose for any data collected after discontinuation from treatment. All listings will include all measurements which will appear in chronological order together with the scheduled nominal days. In all listings dates will be presented in the format ‘YYYY-MMM-DD’ and times will be presented as ‘hh:mm’ or ‘hh:mm:ss’ as needed.

A listing of reasons for screen fail will be provided for participants who fail screening. A listing of reasons for not being dosed will be provided for participants who were randomized but not dosed. will also be provided.

Appropriate descriptive statistics will be provided in summary tables by treatment and Nominal Day for all endpoints, collected or derived. A total column will always be presented.

Figures will be generated to visualise all the raw data (not just those that fall on the nominal days) to aid interpretation of the results as indicated in their respective sub-sections in Section 8.

Treatment labels for TFLs

Full treatment regimen	Summary tables label	Listings label
Group A: Standard of Care + Zilucoplan 32.4mg i.v. + prophylactic antibiotics	Zilucoplan 32.4mg i.v. + Standard of Care	Group A: Zilucoplan 32.4mg i.v. + Standard of Care + prophylactic antibiotics
Group B: Standard of Care + prophylactic antibiotics	Standard of Care	Group B: Standard of Care + prophylactic antibiotics
Notes:	Standard of Care maybe abbreviated to 'SoC' if so add Footnote: SoC=Standard of Care	Standard of Care maybe abbreviated to 'SoC' if so add Footnote: SoC=Standard of Care If the label is still too long for some listings the 'Group A/B' may be dropped'.

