3.5.2 Randomized Set

The Randomized Set (RS) will consist of all participants randomized into the study. This will only be created if any participant was not dosed after randomization.

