3.5.4 Full Analysis Set

The Full Analysis Set will consist of all participants who have received at least 1 dose of Zilucoplan® on Arm A and who have had at least one dose of IV prophylactic antibody on Arm B. This is clearly the same as the SS but the FAS will be referred to when reporting results for efficacy endpoints.

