
Objective 6 All-cause mortality rate at 28 days post randomisation (all treated participants)
 
All-cause mortality rate at 28 days post randomisation (excluding participants that required invasive mechanical ventilation or ECMO, non-invasive mechanical ventilation or high-flow oxygen devices within 24 hours prior to or after randomisation)
 
All-cause mortality rate at 28 days post randomisation (excluding participants that required invasive mechanical ventilation or ECMO within 24 hours prior to or after randomisation)
 
All-cause mortality rate at 28 days post randomisation (excluding participants that required invasive mechanical ventilation or ECMO, non-invasive mechanical ventilation or high-flow oxygen devices within 24 hours prior to or after randomisation)
 
All-cause mortality rate at 28 days post randomisation (only including participants that required invasive
	
Using 6 point ordinal scores, DATES and VITAL SIGNS and SuppO2 variables :
 
Derive indicator variable identifying each sub-group of patients identified in the Endpoint column
 
Derive Mortality variable identifying whether a patient has died within 28 days of randomisation
	
For each mortality sub-group: PROC LOGISTIC Model: Mortality=ACTARM Output percentage died on each treatment and 95% confidence interval. Odds ratio and 95% confidence interval

Endpoint	Derivation	Analysis

mechanical ventilation or ECMO within 24 hours prior to or after randomisation)
 
All-cause mortality at follow up 12-22 weeks post-randomisation for all treated participants
		

Objective 5
 
Incidents of participants in each category of the 6-point ordinal scale at follow-up 12-22 weeks post randomisation
	
6-point ordinal score
	
PROC FREQ to create summary table of actual counts and percentages for each of the 6-points on the ordinal scale at follow-up by treatment arm

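### Efficacy is analysed in dosed participants only, and by treatment received in every set if treatment departs from allocation, so no planned analysis is guaranteed to keep the randomised comparison

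*SAP*

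**What the plan says.** SAP 3.5 assigns all efficacy analyses to the FAS. Repeating them on the Randomized Set or Per Protocol Set is optional and depends on those sets being created.

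FAS membership (SAP 3.5.4) requires "at least 1 dose of Zilucoplan® on Arm A and who have had at least one dose of IV prophylactic antibody on Arm B". The last noun is evidently a slip for antibiotic, the word used in the Safety Set definition (3.5.3). The SAP itself says that the FAS and the Safety Set are the same.

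On grouping, SAP 3.5 starts from an expectation: "It is expected that participants will receive treatment as randomized". If that fails, "then all analysis sets participants will be allocated to the actual treatment they received", and the Randomized Set is named among the as-treated sets. The justification for efficacy is one sentence: "Since this is a PoC study, it is appropriate that treatment assignment for the FAS will be also be actual treatment received".

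Of the Randomized Set, SAP 3.5.2 says: "This will only be created if any participant was not dosed after randomization". SAP 3.1 also plans for such cases: "A listing of reasons for not being dosed will be provided for participants who were randomized but not dosed".

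Mortality follows the same pattern. The endpoint in SAP 2.2.1.2 is "All-cause mortality rate at 28 days post randomisation (all treated participants"), and protocol 4.2 uses the same restriction. The model in SAP Table 8.1 is "PROC LOGISTIC Model: Mortality=ACTARM". ACTARM is not defined, though the name fits the actual-treatment rule. Protocol section 11 defines no analysis sets.

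**The concern.** Randomisation protects the comparison only if patients are kept, and counted, in the arm to which they were allocated. Here entry to the efficacy set depends on an event after randomisation, and that event differs between arms. In an open-label trial of acutely ill patients, whether an Arm A patient receives the first injection can depend on how the patient is doing and on knowledge of the allocation. Entry to Arm B needs only a routine antibiotic.

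The Randomized Set does not repair this. It exists exactly when someone was not dosed, yet its use is optional and it is listed as as-treated. An undosed Arm A patient then has no stated group. Protocol 8.2 gives ceftriaxone to Arm A as well, so an Arm A patient who had the antibiotic but no Zilucoplan has received what qualifies a patient for Arm B. The SAP does not say whether that patient is left out or counted as Arm B.

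Mortality is timed from randomisation but counted in treated patients, so a death between randomisation and the first Zilucoplan dose would not count against Arm A.

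Being a proof-of-concept study does not justify this. The trial is randomised and sized for a two-sided 5% test (SAP 2.4), and it reports p-values for the primary endpoints (SAP 3.1, 8.1.2). Treatment received is the right basis for safety and PK, but that argument does not carry over to efficacy.

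**Working it through.** **Inputs from the documents.** 54 v 27 participants, target difference 80 mmHg (25% of 320), SD 105, two-sided 5%, dropout below 10%, stated power above 85% (protocol 11.1, SAP 2.4).

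**The plan's own figure.** SE = 105 × √(1/54 + 1/27) = 24.7. Two-sample noncentral-t power for 80 mmHg is 89.1% at 54 v 27, and 85.5% at 49 v 24 (10% dropout). The stated figure reproduces, so the sample size is not in question.

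**Assumptions not in the documents.** No true effect; k Arm A patients go undosed; they are the k worst on a prognostic marker correlated 0.5 or 0.8 with outcome; their outcomes are observed; Arm B has no matching loss unless stated. No document gives k.

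**Simulation** (60,000 trials per cell, pooled t-test; each pair is correlation 0.5 / 0.8):

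| Handling of undosed Arm A patients | Bias towards Zilucoplan, mmHg | Two-sided type I error |
|---|---|---|
| Dropped, k=1 | 2.3 / 3.7 | 5.2% / 5.6% |
| Dropped, k=2 | 4.2 / 6.6 | 5.5% / 6.6% |
| Dropped, k=3 | 6.1 / 9.4 | 6.0% / 7.7% |
| Counted as Arm B, k=2 | 11.8 / 18.9 | 7.4% / 11.6% |
| Counted as Arm B, k=3 | 16.3 / 26.1 | 10.2% / 18.3% |
| Matched loss, 2 in A and 1 in B | 0.1 / 0.2 | 5.4% / 5.9% |
| Analysed as randomised | 0.0 | 5.1% |

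As a share of the target, the dropped cases run from 2.3/80 = 3% to 9.4/80 = 12%. For k=2-3 dropped, false positives favouring Zilucoplan are 3.8-6.5% against a nominal 2.5%.

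**Closed-form cross-check.** Let m Arm A patients have outcomes D lower than the rest.
- Dropped: bias = D·m/54. With D = 105 (1 SD), m = 1 and 3 give 1.9 and 5.8 mmHg.
- Counted as Arm B: bias = (D·m/54) × 81/(27+m). With D = 105, m = 2 gives 3.89 × 81/29 = 10.9, and m = 3 gives 5.83 × 81/30 = 15.8 mmHg.

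These are of the same order as the simulated values.

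**28-day mortality, assumed equal in both arms.** At 15%, 8.1 deaths are expected among 54.
- One pre-dose death dropped: 7.1/53, OR = (7.1/45.9)/(0.15/0.85) = 0.88.
- Two dropped: 6.1/52, OR = (6.1/45.9)/(0.15/0.85) = 0.75.

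At 20%, 10.8 deaths are expected.
- One dropped: 9.8/53, OR = (9.8/43.2)/0.25 = 0.91.
- Two dropped: 8.8/52, OR = (8.8/43.2)/0.25 = 0.81.

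**Power cost of analysing as randomised.** If two Arm A patients are untreated and gain nothing, the mean effect is 80 × 52/54 = 77.0 mmHg. Power is 86.8% at 54 v 27 (89.1% undiluted) and 82.8% at 49 v 24 (85.5% undiluted).

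**The case against.** The strongest reply is that the harm is contingent and probably small. The SAP expects treatment as randomised. The protocol 9.4 schedule puts randomisation and first dose on the same day, study staff give the drug (protocol 8.1.6), and patients unlikely to survive 48 hours are excluded (protocol 6.2). SAP section 2 says dosing follows very soon after randomisation. The statement in SAP 2.2.1.2 of about 24 hours between the two may be a slip for the screening window. This stands as a reason to expect a small k, but the SAP leaves the gap unresolved and still provides for undosed patients.

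Second, the largest figures need a strained reading. Regrouping applies to those who received a different treatment, and an undosed patient arguably received none. That is fair: dropping from the FAS is the natural reading, and the Arm B figures show only what the wording permits.

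Third, part of the two-sided error inflation comes from trimming the tail, since matched loss also gives 5.4-5.9%. This is true of the two-sided rate. The bias and the excess of false positives in one direction do not arise from matched loss. If those undosed were instead patients doing well, the bias would run the other way.

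Fourth, patients who die or leave before day 6 give no blood gas, so an as-randomised set would not restore them to the primary model. This stands.

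Fifth, the mortality shift is small against its uncertainty: around an odds ratio of 1.00, the 95% interval is about 0.27-3.65 at 15% mortality and 0.32-3.17 at 20%. Secondary endpoints carry no p-values. Both points hold, but imprecision does not excuse an avoidable bias.

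**Conclusion.** The concern holds and should be fixed. The SAP states a rule under which efficacy is estimated in dosed patients, with a different qualifying dose in each arm, and under which any departure from allocation moves every set to treatment received. No as-randomised efficacy analysis is guaranteed.

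The size depends on events the documents do not quantify. It is zero if all 81 are dosed as allocated, and about zero in bias if losses are in proportion. With one to three of the sickest Arm A patients dropped and none in Arm B, the bias is +2.3 to +9.4 mmHg. The mortality odds ratio moves to 0.75-0.91 if one or two early Arm A deaths are lost. Those figures rest on the stated assumptions about k, prognosis and equal mortality. That the rule can break the randomised comparison follows from the text alone.

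**What to change.** Amend the SAP before database lock:

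1. In 3.5, make the primary efficacy set all randomised participants, analysed by randomised arm.
2. Define the Randomized Set as as-randomised, not as-treated.
3. In Table 8.1, use the randomised arm in place of ACTARM in the efficacy models, and add 28-day mortality in all randomised participants.
4. In 3.2.1 and 3.2.2, anchor day 1 and baseline on randomisation for participants never dosed, since relative day, study periods and baseline are now tied to the first dose.
5. Keep as-treated grouping for safety and PK, and keep the as-treated FAS as a sensitivity analysis for efficacy.

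A lesser change would make the Randomized Set as-randomised and its repeat mandatory whenever anyone is undosed or misallocated. That would guarantee one intact comparison, but the headline result would stay on the dosed-only set.

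The cost is wording and one derivation rule, with no new procedures. If everyone is dosed as allocated, results do not change. Otherwise there is slight dilution, about two to three percentage points of power for two untreated Arm A patients. For patients who die or leave before day 6, the gain is mainly in the mortality and ordinal-scale endpoints.

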3.5.1 Enrolled Set

The Enrolled Set (ES) will consist of all participants who have given informed and will consist of all screened participants, including screen failures.

3.5.2 Randomized Set

The Randomized Set (RS) will consist of all participants randomized into the study. This will only be created if any participant was not dosed after randomization.

3.5.3 Safety Set

The Safety Set (SS) will consist of all participants who have received at least 1 dose of Zilucoplan® on Arm A and all participants who have had at least one dose of IV prophylactic antibiotic on Arm B.

3.5.4 Full Analysis Set

The Full Analysis Set will consist of all participants who have received at least 1 dose of Zilucoplan® on Arm A and who have had at least one dose of IV prophylactic antibody on Arm B. This is clearly the same as the SS but the FAS will be referred to when reporting results for efficacy endpoints.

3.5.5 Completer Analysis Set

The completer analysis set comprises participants who have received treatments per protocol (including patients who are discharged due to clinical improvement prior to completing the specified maximum number of days of treatment) and have complete data available up to D28 or up to date of death, whichever is sooner (Section 5.1)

3.5.6 Per Protocol Set

The Per Protocol Set (PPS) will consist of participants in the FAS without any major protocol deviations that may influence the validity of the data. If there are no major protocol deviations, this analysis set will not be created. This set will not be used for Interim1 as no protocol deviation meeting will have taken place.

3.5.7 Pharmacokinetic Analysis Set

The Pharmacokinetic Set (PKS) will be all participants in Arm A in SS who have at least one evaluable PK concentration.

3.6 Centres

3.6.1 Centre pooling strategy

All by participant listings will include the various centers. Summary statistics of all endpoints will be provided by center and treatment, as well as by treatment. The data from all centers will be pooled for both safety and efficacy summaries. Statistical models may include center as a covariate (center is included as a stratifying factor in the randomization). Centre by treatment interaction may be included if appropriate.

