2.4 Determination of sample size

The outcome(s) on which the sample size calculation is based upon, is the primary endpoint measurement of oxygenation, defined as ratio of PaO₂/FiO₂.

The target difference is the difference from baseline measured at the primary endpoint (at day 6 and day 15) between the control and the treated group. Given a sample size of 81 participants, 54 on Zilucoplan® and standard of care and 27 on standard of care there would be >85% power to show a significant difference from standard of care at the 2 sided 5% level if the true underlying treatment difference was an 80 point difference (25% of 320, being the mean at hospital admission) in the PaO₂/FiO₂ ratio. This assumes a standard deviation of 105 and a dropout rate of less than 10%.

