8.1.2 Primary analysis of the primary efficacy endpoint(s)

Summary descriptive statistics for each endpoint and change from baseline for each endpoint, including to follow-up, will be provided by treatment and Nominal Day (D1(Baseline), D2, D6, D15 and Follow-Up).

Each endpoint (PaO₂/F_iO₂ ratio, P(A-a)/O₂ gradient, a/A PO₂ ratio) will be analyzed separately using a Mixed Model Repeated Measures (MMRM) analysis with fixed effects for Baseline, treatment, Nominal Day (using Nominal Days, D6 and D15), Baseline*Nominal Day interaction and treatment*Nominal Day interaction where Nominal Day is categorical. Participant will be fitted as a random effect and an unstructured covariance will be used, unless it fails to converge,

when other covariance structures will be considered. Mean change from baseline to D6 and D15 for each treatment arm and differences between treatments in mean change from baseline to D6 and D15, their 95% confidence intervals and p-values will be estimated directly from the model.

The primary analysis will not adjust for missing data, other than how they are handled in MMRM under the assumption that the data are missing at random. This assumption implies that the behaviour of the post dropout observations can be predicted from the observed endpoints, and therefore the response can be estimated without bias using exclusively the observed data.

The following results from the model will be tabulated:

- LSMEANS (adjusted for baseline levels) and 95% confidence intervals for change from baseline by treatment and Nominal Day for each endpoint (PaO₂/FiO₂ ratio, P(A-a)/O₂ gradient, a/A PO₂ ratio)
- Estimates of the differences between treatments in mean change from baseline, 95% confidence interval and p-value at D6 and D15 for each endpoint (PaO₂/FiO₂ ratio, P(A-a)/O₂ gradient, a/A PO₂ ratio).
- Mean percentage change from baseline will be estimated from the results of the MMRM model for D6 and D15 for each Treatment Arm, together with 95% confidence intervals.

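### Randomisation is stratified by centre, but the plan leaves centre optional in the primary model; if centre is prognostic, modest precision is forgone, and the choice stays open after data are seen

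*SAP*

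**What the plan says.** SAP 3.4 states "The 2:1 randomisation will be carried out using REDCap (electronic IWRS system) by centre" and plans no other stratification factor. SAP 3.6.1 confirms the role of centre and makes adjustment optional: "Statistical models may include center as a covariate (center is included as a stratifying factor in the randomization". It adds that a centre-by-treatment interaction may be fitted where appropriate. It gives no criterion or deadline for either decision and, despite its heading, no rule for combining small centres.

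SAP 8.1.2 specifies the primary model as a mixed model for repeated measures, an "analysis with fixed effects for Baseline, treatment, Nominal Day (using Nominal Days, D6 and D15", plus the baseline-by-day and treatment-by-day interactions. Centre is not among the terms. It is also missing from the covariates listed in SAP 4.1 and from the covariate sensitivity analysis in SAP 8.1.3. Protocol 9.1 and 11.2 mention neither stratification by centre nor a centre term.

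SAP 8.1 says that residuals will be plotted against potential covariates and that the results of whichever analysis proves most appropriate will be the ones presented.

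**The concern.** When patients are allocated in balance within centres, differences between centres largely cancel out of the treatment comparison. A model with no centre term still counts those differences as residual noise. Its standard error then exceeds the true one, the interval is conservative, and precision secured by the randomisation is not used.

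The second issue is pre-specification. The trial is open-label, and the supplier of the drug does the analysis (Protocol 7.2 and 11.3). The primary endpoints are analysed at Interim 1 and may be final at Interim 2 (SAP 4.4). Because 3.6.1 is permissive and 8.1 selects the most appropriate analysis, whether centre enters the model could be settled once the arms have been compared. The primary endpoints carry p-values (SAP 3.1), so the choice matters.

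**Working it through.** **Inputs from SAP 2.4.** "Given a sample size of 81 participants, 54 on Zilucoplan® and standard of care and 27 on standard of care"; difference 80 points in PaO₂/FiO₂; SD 105; two-sided 5%; dropout below 10%; stated power above 85%.

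**Inputs not in the documents (assumed).** Share ρ of outcome variance due to centre, 0 to 0.20; number of centres, 4 to 12 (SAP 2.3 says only that there are several); blocks of three within centre; uneven centre sizes.

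**Step 1: reproduce the plan's power.** With 10% dropout, 27 × 0.9 = 24.3 controls and 54 × 0.9 = 48.6 active patients.

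- SE = 105 × √(1/24.3 + 1/48.6) = 26.09.
- 80/26.09 = 3.067, and Φ(3.067 − 1.96) = Φ(1.107) = 86.6%. The noncentral t gives 85.7%.
- With all 81 evaluable, power is 89.8% (t: 89.1%).

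The stated figure reproduces.

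**Step 2: effect of omitting centre, by formula.** Hold the total SD at 105 and assume exact balance within centre. The true SE is then √(1−ρ) times the SE reported by the model without centre.

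- Excess width = 1/√(1−ρ) − 1
- Power without centre = Φ[(80/SE − 1.96)/√(1−ρ)]
- Power with centre = Φ[80/(SE√(1−ρ)) − 1.96]
- Type I error without centre = 2Φ(−1.96/√(1−ρ))

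Example at ρ = 0.10: √0.9 = 0.9487. Excess width is 1/0.9487 − 1 = 5.4%. Power without centre is Φ(1.107/0.9487) = 87.8%. Power with centre is Φ(3.067/0.9487 − 1.96) = 89.8%.

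| ρ | Interval too wide by | Power without centre | Power with centre | Type I error without centre |
|---|---|---|---|---|
| 0 | 0% | 86.6% | 86.6% | 5.0% |
| 0.02 | 1.0% | 86.8% | 87.2% | 4.8% |
| 0.05 | 2.6% | 87.2% | 88.2% | 4.4% |
| 0.10 | 5.4% | 87.8% | 89.8% | 3.9% |
| 0.20 | 11.8% | 89.2% | 92.9% | 2.8% |

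These are upper-end figures, because they charge nothing for estimating the centre terms. Power without centre never falls below Step 1, since SD 105 already contains any centre variance.

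**Step 3: simulation with unpooled fixed centre effects.** 81 patients, 10% dropout, one time point, no baseline covariate, 4,000 trials per setting; error about 0.5 points on power.

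| Centres | ρ | Width without centre relative to with | Power without centre | Power with centre |
|---|---|---|---|---|
| 4 | 0.10 | +3.2% | 87.3% | 88.7% |
| 8 | 0.05 | +0.7% | 87.1% | 87.1% |
| 8 | 0.20 | +8.3% | 88.8% | 91.8% |
| 12 | 0.02 | −1.6% | 85.9% | 83.7% |

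With many small centres and little centre effect, unpooled fixed effects cost more than they recover.

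**Step 4: simulation with a random intercept for centre.** Same design, 1,500 trials per setting; error about 0.9 points on power.

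| Centres | ρ | Power without centre | Power with random intercept |
|---|---|---|---|
| 12 | 0 | 84.9% | 85.5% |
| 12 | 0.02 | 84.9% | 85.9% |
| 12 | 0.10 | 85.9% | 88.1% |
| 12 | 0.20 | 88.5% | 91.3% |
| 8 | 0.10 | 89.1% | 90.3% |
| 8 | 0.20 | 88.1% | 92.0% |
| 5 | 0.10 | 88.1% | 89.9% |
| 5 | 0.20 | 89.5% | 92.7% |

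No setting lost power. At ρ = 0.20 type I error was 5.1–5.5% with the random intercept and 3.3–3.7% without centre. A further simulation over 5, 8 and 12 centres agreed. The random intercept gained about 1–3 points at ρ = 0.10 and 3–4 at 0.20. Unpooled fixed effects lost about 1–2 points with 12 centres and ρ of 0.05 or less.

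**The case against.** The strongest reply is that every figure above depends on quantities the documents do not give.

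- **Between-centre variance.** If it is zero, nothing is lost. The primary model adjusts for baseline, so if centres differ mainly in severity at entry, much of the centre effect is already removed. The share that matters is what remains after baseline, and the simulations had no baseline covariate and only one visit. This stands, and it is why the result is conditional.
- **Balance within centre.** The upward bias in the standard error needs restricted allocation within centre. The SAP says randomisation is by centre but gives no block size. Without such restriction only an efficiency argument remains. This stands too.
- **Size and direction.** The effect is small and conservative, and the trial is a phase 2a proof of concept. This is correct.
- **The two complaints pull apart.** If 8.1.2 fixes a model without centre, there is no open choice; if 3.6.1 governs, centre has not been left out. The documents do not say which section prevails, so the fair description is that the matter is unsettled. Centre is not ignored either, since 3.6.1 plans summaries by centre and treatment.

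A reader might infer that the interval is certainly too wide, or that the trial is underpowered. The documents support neither. The first depends on unstated variance and balance, and the stated power reproduces with no centre term.

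**Conclusion.** The plan stratifies on centre but does not commit to analysing by it. Given balanced allocation within centre and a centre effect that persists after baseline adjustment, the model without centre is conservative. At an assumed variance share of 0.05–0.10 the interval is roughly 2–5% too wide and about 1–3 points of power are forgone. At 0.20 the interval is about 8–12% too wide (simulation to formula) and 3–4 points are forgone. At zero there is no loss. The power claim in SAP 2.4 is not breached, and omission alone does not raise the false-positive rate.

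The gain in precision is modest, so the pre-specification gap carries at least as much weight. The wording permits a choice after comparative results are seen. Nothing in the documents shows that such a choice is intended. The analyst is the drug's supplier, whereas the sponsor is the university hospital, so the freedom should not be described as the sponsor's.

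**What to change.** In SAP 8.1.2, include centre of randomisation in the primary model for all three oxygenation measures. A random intercept is preferable. The alternative is a fixed effect with small centres pooled by a rule written down before comparative data are seen. Specify the centre of randomisation, because SAP 3.6.2 expects some patients to change hospital. In SAP 3.6.1, change *may include* to *will include* for the primary model. Report the model without centre as a sensitivity analysis.

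The cost is a sentence or two in the SAP and a slightly more complex model. The one form to avoid is unpooled fixed effects, which could cost 1–2 points of power if there are many small centres and little centre effect.
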